3.2. Standard Calculations

Standard calculations are described as follows:

Age:

If age is not collected on the electronic case report form (eCRF), age at screening will be calculated in years using the date of birth and the date of the Screening visit (Visit 1), rounded down to the nearest integer.

Duration:

Duration between two dates date1 and date2 will be calculated as follows:

date2 – date1 + 1, when expressed in days

(date2 – date1 + 1)/7, when expressed in weeks

(date2 – date1 + 1)/365.25, when expressed in years

Change/Percent Change from Baseline:

Change from baseline will be calculated as: Value at post-baseline visit – value at baseline

Percent change from baseline will be calculated as: (Change from baseline/value at baseline) * 100%

Note: Change from baseline summaries will only include subjects with a baseline value and at least one post-baseline value. If the value at baseline is 0, percent change from baseline will be missing.

Study Day:

Study day will be calculated as follows:

assessment date – date of the first dose of study treatment, where assessment date < date of the first dose of study treatment

assessment date – date of the first dose of study treatment + 1, where assessment date \geq date of the first dose of study treatment

Date Imputation:

If complete dates are unavailable, July 2 (midpoint of a non-leap year) will be utilized in calculations in cases where both month and day are missing, and the 15th will be utilized in calculations in cases where only day is missing.

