5.3. Randomization Criteria

Subjects must fulfill the following criteria to be randomized to study treatment:

1. **Diary compliance:** Compliance with completion of the Diary as defined as:
 - a. Completion of questions on 4 or more of the last 7 days immediately prior to Visit 2 (includes the morning of Visit 2).
 - b. **Note:** If the Diary was completed on < 4 days due to technical challenges, the Visit 2 may be delayed up to an additional 3 days to allow for completion of the Diary parameters above.
2. **Eosinophilic Phenotype:** Subjects must meet at least one of the criteria below.
 - Blood eosinophil count ≥ 250 cells/ μ L obtained at Visit 1.
OR
 - Minimum NPS of 4 out of a maximum score of 8 with a score of at least 2 for each nostril as assessed by a blinded central reader. Subjects with an NPS of 1-3 are not eligible for randomization.
3. **CRS exacerbation:** Subjects who experience a CRS exacerbation during the Run-in period should have their Randomization Visit (Visit 2) delayed until the investigator considers the subject has returned to their baseline status. If a 4-week Run-in period has elapsed before the subject is back to baseline status, then the subject will be considered a Run-in failure. CRS exacerbation is defined in [Section 8.1.6](#).
4. **Laboratory abnormality:** No evidence of clinically significant abnormality in the hematological, biochemical, or urinalysis at Screening visit, as judged by the investigator.
5. **Hepatitis status:** No diagnosis of chronic hepatitis B or C, as evidenced by a negative hepatitis B surface antigen (HBsAg) or hepatitis C antibody screen at Screening visit.
6. **Chemistry and hematology obtained at Screening visit:**
 - ALT $\leq 1 \times$ the upper limit of normal (ULN)
 - AST $\leq 1 \times$ ULN
 - Alkaline phosphatase $< 2 \times$ ULN
 - Bilirubin $< 1 \times$ ULN
 - Absolute eosinophil count $< 1,500$ cells/ μ L
 - White blood cell count $< 15,000$ cells/ μ L
7. **Pregnancy test:** For WOCBP, both the serum pregnancy test at the Screening visit and the urine pregnancy test at Visit 2 must be negative.
8. **Use of MFNS:** Subject newly switched onto MFNS during screening should tolerate MFNS during Run-in.
9. **Nasal symptoms:** SNOT-22 score ≥ 17 as assessed at randomization.
10. **ECG overread:** ECG overread by the central ECG reader confirms the QTcF interval is < 450 msec for males or QTcF < 470 msec for females.

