3.3. Considerations Related to the COVID-19 Pandemic

Screening of subjects for this study began in April 2019, and the last subject completed their participation in the study in August 2020. As such, a portion of this study's conduct was affected by the global Coronavirus Disease 2019 (COVID-19) pandemic.

At the time of finalization of this SAP in September 2020, several regulatory authorities have issued guidance related to trial conduct and associated methodological issues related to the effect of the COVID-19 pandemic, including, but not limited to, the Food and Drug Administration (FDA) ([References: FDA Guidance on Conduct of Clinical Trials of Medical Products during COVID-19 Pandemic, March 2020, updated on July 2, 2020](#) and [Statistical Considerations for Clinical Trials During the COVID-19 Public Health Emergency, June 2020](#)) and European Medicines Agency (EMA) ([References: Guidance on the Management of Clinical Trials during the COVID-19 \(Coronavirus\) pandemic, Version 3 \(28/04/2020\)](#) and [Points to consider on implications of Coronavirus disease \(COVID-19\) on methodological aspects of ongoing clinical trials, 26 June 2020](#)).

Potential effects on conduct of this study related to the COVID-19 pandemic include, but are not limited to, the following: subject discontinuation of study treatment and/or withdrawal from study; inability or reduced ability for subjects to continue on IP due to disruptions in IP dispensing; missed visits or missed assessments; alternative procedures (e.g., telephone visit or virtual visit) used for collection of critical efficacy and/or safety assessments; and inability for sites to complete entry of data in the electronic case report form (eCRF) and/or collect data via other sources (e.g., eDiary).

A determination will be made at the end of study if additional statistical analyses are warranted as part of the final analysis, should participation of subjects or endpoint ascertainment be affected by the COVID-19 pandemic to a substantial degree. These additional analyses would be undertaken to enable an understanding of the potential impact of the COVID-19 pandemic on study results.

A non-exhaustive list of examples of such additional analyses is as follows:

- Analysis of compliance:
 - By subgroup of subjects who received direct IP shipment due to the COVID-19 pandemic versus those that did not
- Analyses of primary and select secondary efficacy endpoints:

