8.3.2.2. Time to Event Endpoints

Time to first response in NPS is defined as the time from the date of the first dose of study treatment to the first date with ≥ 1 point improvement in NPS from baseline for subjects in the randomized CRSwNP stratum. Subjects in the randomized CRSwNP stratum who do not experience ≥ 1 point improvement in NPS from baseline will be censored at their last post-baseline NPS assessment, or on Day 1 if no baseline NPS assessment or no post-baseline NPS assessment was performed.

CRS exacerbation is defined as deterioration of CRS symptoms requiring treatment with an antibiotic, an anti-inflammatory drug, or a symptom reliever; an Emergency Department visit; or hospitalization (Kuiper, 2018). Time to first CRS exacerbation is defined as the time from the date of the first dose of study treatment to the first date of treatment with an antibiotic, an anti-inflammatory drug, or a symptom reliever, the date of Emergency Department visit, or the date of hospitalization, whichever occurs first. Subjects without a CRS exacerbation will be censored at their last post-baseline CRS exacerbation assessment, or on Day 1 if no post-baseline CRS exacerbation assessment was performed.

For the primary analysis of both time to event endpoints, all data through Week 16 will be included; a sensitivity analysis of both time to event endpoints will be performed including all data.

The number and proportion of subjects with a response in NPS will be summarized for subjects in the randomized CRSwNP stratum. Time to first response in NPS will be compared between treatment groups using a Cox proportional hazards model and will include covariates for treatment group, disease status stratification factor values used for randomization (CRSwNP with comorbid asthma, CRSwNP without comorbid asthma, and CRSsNP), region (United States, Eastern Europe), and baseline NPS.

The number and proportion of subjects with CRS exacerbations will be summarized. Time to first CRS exacerbation will be analyzed using a Cox proportional hazards model and will include covariates for treatment group, disease status stratification factor values used for randomization (CRSwNP with comorbid asthma, CRSwNP without comorbid asthma, and CRSsNP), and region (United States, Eastern Europe).

The exact method will be used to handle ties in event times.

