8.3.3.3. Annualized Rate of CRS Exacerbations

The date of onset of a CRS exacerbation will be considered to be the first date of treatment with an antibiotic, an anti-inflammatory drug, or a symptom reliever, the date of Emergency Department visit, or the date of hospitalization, whichever occurs first. The end date of a CRS exacerbation will be considered to be the last date of treatment with an antibiotic, an anti-inflammatory drug, or a symptom reliever, or 6 days after the date of onset (for a total duration of 7 days), whichever is later. Courses of treatment separated by 7 or more days will be counted as separate exacerbations.

The number and proportion of subjects with 0, 1, and ≥ 2 CRS exacerbations and the adjusted annualized rate of CRS exacerbations will be summarized by treatment group. The unadjusted annualized rate of CRS exacerbations will be calculated as the total number of CRS exacerbations divided by the total number of subject-years of follow-up and will also be summarized by treatment group.

The total number of CRS exacerbations will be analyzed using a negative binomial regression model, with the logarithmic transformation of follow-up time as the offset parameter. The follow-up time is defined as the subject's time on study through Day 120. The model will include terms for treatment group, disease status stratification factor values used for randomization (CRSwNP with comorbid asthma, CRSwNP without comorbid asthma, and CRSsNP), and region (United States, Eastern Europe). If the distribution of CRS exacerbation data is underdispersed, or if the negative binomial regression model fails to converge, a Poisson regression model will be used instead of the negative binomial regression model.

The rate ratio for the GB001 40 mg group versus placebo, corresponding 95% CI, and p-value will be provided from the model. The percentage reduction and corresponding 95% CI will also be provided.

Lastly, the subject CRS exacerbation rate will be calculated as the number of CRS exacerbations for each subject divided by the number of years followed in the study for that subject and will be summarized by treatment group.

Analyses of annualized rate of CRS exacerbations may also be presented by various time periods (Baseline through Week 8, Week 8 through Week 16, and Baseline through Week 20 [Follow-up]) in order to elucidate onset and durability of effect over time.

CRS exacerbation data will also be presented in by-subject data listings.

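### Partial dates are imputed without bounds, so a CRS exacerbation that follows first dose can be given an onset date before it

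*SAP*

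**What the plan says.** SAP 3.2 gives one general rule for incomplete dates. With the day missing, "the 15th will be utilized in calculations in cases where only day is missing". With month and day missing, "July 2 (midpoint of a non-leap year) will be utilized in calculations in cases where both month and day are missing". Neither part refers to first dose, visit dates, a recorded end date or last contact. The same section defines a duration in days as "date2 – date1 + 1, when expressed in days".

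SAP 8.3.2.2 sets the time origin of the secondary endpoint: "Time to first CRS exacerbation is defined as the time from the date of the first dose of study treatment". SAP 8.3.3.3 fixes onset for the exploratory annualized rate: "The date of onset of a CRS exacerbation will be considered to be the first date of treatment with an antibiotic", or the date of an equivalent treatment, an emergency visit or a hospitalization if that comes first. Neither section adds a rule for partial dates, so 3.2 governs.

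The SAP does protect other records. An adverse event with an incomplete start date defaults to treatment-emergent (9.1), and a medication of unclear timing defaults to concomitant (6.8). Both rules classify records; neither assigns an onset date to an exacerbation. Protocol 8.3.7 keeps non-serious exacerbations out of the adverse event data, so the 9.1 default does not reach them.

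**The concern.** The date is what separates a run-in exacerbation from an on-treatment one, and run-in exacerbations are expected (Protocol 5.3): "Subjects who experience a CRS exacerbation during the Run-in period should have their Randomization Visit (Visit 2) delayed". When the day is missing, the 15th can fall on the wrong side of first dose even though the visit at which the event was reported shows which side is correct.

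Three errors can follow:

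- A post-dose event is dated before Day 1.
- An event late in the treatment period is dated beyond it.
- A run-in event, in a subject first dosed on or before the 15th, is dated after dosing.

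The plan can also contradict itself: an antibiotic may be classed as concomitant under 6.8 while the exacerbation it defines is dated before dosing under 3.2. With about 100 subjects, how a misdated first event is handled should not be left to the programmer.

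**Working it through.** The documents give no expected number of exacerbations, no power for this endpoint and no frequency of partial dates, so there is no planned figure to reproduce. The check applies the SAP 3.2 formulas to examples and then enumerates dates. Every share below is conditional on the date being partial.

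**Worked example, post-dose event.** First dose 20 Sep 2019; exacerbation treated 26 Sep 2019, day not recorded.
- True time: 26 − 20 + 1 = 7 days.
- Imputed onset 15 Sep (study day 15 − 20 = −5). Time: 15 − 20 + 1 = −4 days.

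A first dose on the 16th gives 15 − 16 + 1 = 0, and on the 31st 15 − 31 + 1 = −15. The error therefore needs a first dose on day 16 or later.

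**Worked example, run-in event.** First dose 12 Sep; run-in event 2 Sep, day not recorded. Imputed onset 15 Sep. Time: 15 − 12 + 1 = 4 days, so it appears as an on-treatment event.

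**Share within the month of first dose.** Take an L-day month and all pairs with event day on or after dose day, equally weighted. There are L(L+1)/2 pairs, of which (L−15)(L−14)/2 have first dose after the 15th.
- L = 28: 91/406 = 22.4%
- L = 29: 105/435 = 24.1%
- L = 30: 120/465 = 25.8%
- L = 31: 136/496 = 27.4%

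**Share over the treatment period.** SAP 3.3 gives the calendar: "Screening of subjects for this study began in April 2019, and the last subject completed their participation in the study in August 2020". Assumed first-dose dates were 1 May 2019 to 15 Apr 2020, or 1 Jun 2019 to 31 Mar 2020, with uniform first-dose and event days through Day 113 (the Week 16 target, 16 × 7 + 1) or Day 120 (the efficacy window limit).

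| First-dose calendar | Through day | Event in month of first dose | Of those, dated pre-dose | Dated pre-dose, all events | Dated after the period |
|---|---|---|---|---|---|
| May–Apr | 113 | 14.2% | 25.1% | 3.6% | 2.9% |
| May–Apr | 120 | 13.4% | 25.1% | 3.4% | 2.9% |
| Jun–Mar | 113 | 13.9% | 26.7% | 3.7% | 3.0% |
| Jun–Mar | 120 | 13.1% | 26.7% | 3.5% | 2.9% |

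The fifth column is the product of the third and fourth; for example, 14.2% × 25.1% = 3.6%.

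For year-only dates, July 2 falls before first dose for 35-41% of event days and after the period for 35-42%.

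**Illustrative count.** If there were 25-40 first exacerbations and 1-10% lacked the day (both assumed), the expected number dated before dosing would run from 25 × 1% × 3.4% = 0.01 to 40 × 10% × 3.7% = 0.15.

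**With a lower bound at first dose.** None of the enumerated events with a missing day is dated before first dose. The September example becomes 1 day (true value 7). Mean absolute dating error hardly moves, from 7.6 to 7.4 days: the bound removes impossible dates but does not recover the true day.

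**The case against.** The best defence is that partial dates should be rare, above all where the rule does harm. The Schedule of Activities reviews exacerbations weekly up to Week 4, so an event in the month of first dose would usually be asked about within about a week. Onset is a treatment, emergency visit or admission date; Protocol 6.5 requires medication start and end dates, and Protocol 10.1.5 provides for source data verification. A year-only date for such an event is close to theoretical. This stands, and it is why the point is minor. It does not make missing days impossible: later reviews are four weeks apart, SAP 3.3 anticipates missed visits and incomplete data entry during the pandemic, and the minimum contact after a missed visit (Protocol 10.11) does not name the exacerbation review.

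Four stronger readings are tempting and not supported.

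- A reader might infer that about half of month-of-first-dose events are affected, because 46-52% of calendar days fall after the 15th (13/28 to 16/31). But a post-dose event must fall on or after first dose, and late dosing leaves few such days in the month; hence 22-27%.
- A reader might infer that the plan discards these events. It does not say so. The event might be dropped, the subject censored, or a later exacerbation counted as the first; the SAP is silent.
- A reader might see a conflict between an event dated after the last assessment and the censoring rule. That rule reads "Subjects without a CRS exacerbation will be censored at their last post-baseline CRS exacerbation assessment" and does not apply to subjects with an event. A date past Week 16 does leave the primary analysis, but the prespecified all-data sensitivity analysis in 8.3.2.2 keeps it.
- A reader might express each misdated event as a percentage of the statistical information. That needs an event count, and the documents give none.

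**Conclusion.** The gap is real and small. Followed as written, SAP 3.2 can give an exacerbation known to be post-dose an impossible pre-dose onset, and nothing elsewhere corrects it. This is a stated rule that yields a wrong event time, not merely a missing detail.

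The percentages rest on uniform first-dose and event days and, for the period-wide figures, on the assumed first-dose calendars. How often dates are partial is unknown and probably low. Time to first exacerbation is a secondary endpoint and the annualized rate an exploratory one; the primary SNOT-22 analysis does not use these dates. Nothing in the documents points to a difference between arms in misdating.

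**What to change.** Add a rule to SAP 3.2, or to 8.3.2.2 and 8.3.3.3, for exacerbation dates:

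- When the event is first reported after dosing, the imputed onset is no earlier than the later of first dose and the previous exacerbation review without the event.
- The imputed onset is no later than the visit at which the event was reported, the recorded end date or last contact, whichever comes first.
- An event reported at or before the pre-dose review at Visit 2 remains a run-in event. This needs its own clause, because a cap at Visit 2 alone would place the event on Day 1.
- The unbounded midpoint rule is kept for history durations only, such as years since surgery or duration of CRS.

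The cost is a few lines of text and a min/max in the code, with no new data. By the SAP's own account it was finalized in September 2020, before unblinding and after the last subject finished. The number of partial exacerbation dates could therefore have been counted blinded; reporting that number would show whether the rule was ever used.

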3.3. Considerations Related to the COVID-19 Pandemic

Screening of subjects for this study began in April 2019, and the last subject completed their participation in the study in August 2020. As such, a portion of this study's conduct was affected by the global Coronavirus Disease 2019 (COVID-19) pandemic.

At the time of finalization of this SAP in September 2020, several regulatory authorities have issued guidance related to trial conduct and associated methodological issues related to the effect of the COVID-19 pandemic, including, but not limited to, the Food and Drug Administration (FDA) ([References: FDA Guidance on Conduct of Clinical Trials of Medical Products during COVID-19 Pandemic, March 2020, updated on July 2, 2020](#) and [Statistical Considerations for Clinical Trials During the COVID-19 Public Health Emergency, June 2020](#)) and European Medicines Agency (EMA) ([References: Guidance on the Management of Clinical Trials during the COVID-19 \(Coronavirus\) pandemic, Version 3 \(28/04/2020\)](#) and [Points to consider on implications of Coronavirus disease \(COVID-19\) on methodological aspects of ongoing clinical trials, 26 June 2020](#)).

Potential effects on conduct of this study related to the COVID-19 pandemic include, but are not limited to, the following: subject discontinuation of study treatment and/or withdrawal from study; inability or reduced ability for subjects to continue on IP due to disruptions in IP dispensing; missed visits or missed assessments; alternative procedures (e.g., telephone visit or virtual visit) used for collection of critical efficacy and/or safety assessments; and inability for sites to complete entry of data in the electronic case report form (eCRF) and/or collect data via other sources (e.g., eDiary).

A determination will be made at the end of study if additional statistical analyses are warranted as part of the final analysis, should participation of subjects or endpoint ascertainment be affected by the COVID-19 pandemic to a substantial degree. These additional analyses would be undertaken to enable an understanding of the potential impact of the COVID-19 pandemic on study results.

A non-exhaustive list of examples of such additional analyses is as follows:

- Analysis of compliance:
 - By subgroup of subjects who received direct IP shipment due to the COVID-19 pandemic versus those that did not
- Analyses of primary and select secondary efficacy endpoints:

- By subgroup of subjects whose study participation was affected by the COVID-19 pandemic versus was not affected;
- Excluding only data that is missing for reasons related to the COVID-19 pandemic (but including imputation of data missing for other reasons); and
- By subgroup of subjects who had an alternative method of collection for an assessment contributing to a particular endpoint (e.g., SNOT-22 completed by subject at home via virtual visit) versus subjects who did not have an alternative method of collection
- Analysis of AEs:
 - Incidence of AEs by subgroup of subjects whose study participation was affected by the COVID-19 pandemic versus was not affected;
 - Incidence of AEs that were collected via an alternative method versus incidence of AEs that were not collected via an alternative method
- Analysis of laboratory values:
 - By subgroup of subjects whose study participation was affected by the COVID-19 pandemic versus was not affected;
 - Excluding values resulting from local collection due to reasons related to the COVID-19 pandemic; and
 - Including only values resulting from local collection due to reasons related to the COVID-19 pandemic

In addition, by-subject listings indicating subjects whose study participation was affected by the COVID-19 pandemic, subjects with missing data related to the COVID-19 pandemic, and/or subjects with an alternative method of collection for specific assessments may be provided.

